## 6. Study Objectives and Purpose

[figure not shown]
- Primary objective: To assess 24-month long-term weight loss in a patient-only vs. partner-assisted intervention.
- Secondary objective: To assess 24-month long-term self-reported patient caloric intake and physical activity in a patient-only vs. partner-assisted intervention.
- Exploratory objective: The role of theoretically hypothesized mediators of intervention effects will be examined, including transformation of motivation, couple efficacy, outcome efficacy, use of communal coping, and social support for physical activity and dietary intake at 24 months.

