### 10. Study Analysis

#### 10.1 Sample Size Determination

The sample size estimate is based on the primary hypothesis that estimated patient weight will be at least 2.5 kg lower at 24 months in the partner-assisted than patient-only arm. This effect size was chosen because smaller differences are unlikely to be considered meaningful to researchers, providers, or patients.(78) The sample size was determined by multiplying the number of participants required for a t-test of post scores by 2(1-p) and adding one extra participant per arm.(79) Based on MAINTAIN, we anticipate a common standard deviation of 19.9 kg and a correlation (p) between the *month0* and *month24* time points of 0.96. Thus, we need 160 participants total (80 in each arm) to detect a 2.5 kg difference with 80% power and a type-I error rate of 5%. We further inflate the sample size to 1) incorporate the intra-class correlation (ICC) of small group members into consideration and 2) compensate for attrition using procedures for group-randomized designs.(66) Let  $m=15$  (conservative upper limit) be the number of patients in each of the small groups, and let  $ICC=0.01$  represent the intra-class correlation between patients in the same group. The updated sample size is  $n = 160 * [1 + (m-1)ICC]$ , or 180. We then conservatively inflate the sample size for an attrition rate of 20% through month24. Therefore, we will enroll  $n=230$  patients (115 per arm), randomized to receive the partner-assisted or patient-only intervention, to detect a 2.5 kg difference in mean 24-month net weight loss between arms.

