
where *trt* is the treatment indicator and *t* is linear time, then the null hypothesis is  $H_0: \beta_3 = 0$ . In addition, we will tabulate the analysis results for the (fixed) effects of the baseline covariates such as patient sex, patient BMI, and partner BMI.

**Aim 2: Test the hypotheses that average daily caloric intake is significantly lower, and frequency of moderate intensity physical activity is significantly greater, in the partner-assisted arm than the patient-only arm at 24 months.** Dietary adherence will be operationalized as daily intake of calories at months 0, 6, 12, 18, and 24. For each of these same assessment times, physical activity will be summarized as the total and mean minutes of moderate levels per week. Changes in dietary adherence and physical activity will be analyzed using the same methods and models as presented for the Aim 1 analyses of weight loss. Previous experience with these outcomes has shown they are often non-normally distributed; therefore, outcomes may be analyzed as generalized linear mixed models, estimated with adaptive Gaussian quadrature, as needed. As exploratory analyses, we will use the models described for Aims 1 and 2 to examine "spillover" effects(34) of the partner-assisted intervention on partner weight and dietary adherence.(50)

**Aim 3: Assess the extent to which interdependence constructs (transformation of motivation, couple efficacy, outcome efficacy, use of communal coping) mediate the effect of the partner-assisted weight management intervention on weight loss.** We will estimate the extent to which the effect of the partner intervention,  $T_i$  on participants' weight at 6 months,  $Y_i$ , is jointly mediated by a vector of five mediating constructs,  $M_i = (M_{i1}, \dots, M_{i5})$  measured at 3 months: transformation of motivation, couples' efficacy, outcome efficacy, use of communal coping, and social support. Each mediating construct is measured by the summary scale of associated items. We will assess mediation twice: separately for the diet and physical activity domains of the mediators.

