Mediation analysis requires additional assumptions beyond treatment randomization, most importantly: (i) no unobserved mediator-outcome confounders; and (ii) no observed mediator-outcome confounder is affected by the intervention. In order to render assumption (i) more plausible, we will make statistical control for a vector of baseline values,  $B_i$  of the blocking variables, weight, and the mediating constructs, and we will assume that the block of mediators referring to diet and the block referring to physical activity do not affect each other (we do, however, permit that the elements of each  $M_i$  affect each other).

We will follow VanderWeele and Vansteelandt's approach to estimate the natural direct effect (NDE) and the natural indirect effect (NIE) of the intervention relative to a set of mediators,  $M$ , by estimating a set of regression equations.  $E[Y_i | T, M, B] = a_0 + a_1 T_i + a_{21} M_{i1} + \dots + a_{25} M_{i5} + a_3 B_i$

$$E[M_{ik} | T, B] = b_{0k} + b_{1k} T_i + b_{2k} B_i \text{ for } k = 1, \dots, 5.$$

We write  $Y_i(t, M_i(t'))$  for the potential outcome of  $i$  if  $i$  received intervention  $t$  and the value the mediators if  $i$  received intervention  $t'$ . Under assumptions (i), (ii), successful randomization of the intervention (all condition on  $B$ ), and correct functional form, we will then estimate the average natural direct effect of the intervention (versus not) on weight at 6 months as

$$E[Y_i(1, M_i(0)) - Y_i(0, M_i(0))|B] = a_1$$

and the natural indirect (mediation) effect as

$$E[Y_i(0, M_i(0)) - Y_i(0, M_i(1))|B] = b_{11}a_{21} + \dots + b_{15}a_{25}.$$

We will bootstrap the standard errors for the direct and indirect effects.

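### Aim 3 bootstraps only standard errors; percentile limits from the same draws would give the joint indirect effect a somewhat more powerful interval at no cost

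*Combined protocol and SAP*

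**What the plan says.** Section 10.2 (Aim 3) asks how far the arm effect on weight at 6 months is "jointly mediated by a vector of five mediating constructs", measured at 3 months. It estimates the effects "by estimating a set of regression equations": one for weight on arm, the five mediators and baseline covariates, and one for each mediator on arm and baseline covariates. The natural direct effect is the single coefficient a1. The natural indirect effect is b11·a21 + ... + b15·a25. The analysis is done twice, once for the diet and once for the physical activity domain of the mediators.

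The only sentence on uncertainty is "We will bootstrap the standard errors for the direct and indirect effects". The text gives no interval type, decision rule, number of draws or resampling unit. Section 6 lists mediation as an exploratory objective ("The role of theoretically hypothesized mediators of intervention effects will be examined"), and no power is stated for it. The reference list (item 85) includes a paper comparing inferential tests of the indirect effect, but Section 10.2 does not cite it. Section 18 lists a Statistical Analysis Plan as an attachment; the text available holds no further detail on Aim 3.

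**The concern.** A bootstrap that delivers only a standard error points to a symmetric normal interval. That suits a1, an ordinary regression coefficient. It suits a sum of products less well. If mediation is present, the bootstrap distribution has its longer tail away from zero, so the limit nearer zero is placed too far from the estimate and the interval includes zero more often than it need. The draws that show this shape will already have been made; reducing them to one number discards it. At stake is some avoidable loss of sensitivity in the only planned test of the trial's mechanism hypothesis (H3).

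**Working it through.** **1. The plan's own figures.** Section 10.1 sizes the trial for the primary outcome only. With SD 19.9 kg, a 2.5 kg difference, 80% power and 5% type I error (two-sided assumed), a t-test of post scores needs 994.6 per arm. Then 994.6 × 2(1 − 0.96) = 79.6, plus 1 = 80.6 per arm, or 161 to 162 in total (160 stated). The design effect gives 160 × [1 + 14 × 0.01] = 182.4 (180 stated). Attrition gives 180/0.8 = 225, or 183/0.8 = 229 (230 stated). The plan's figure is reproduced closely enough. It has no counterpart for Aim 3.

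**2. Analysable number.** The trial enrols 230 "patients (115 per arm), randomized to receive the partner-assisted or patient-only intervention". On attrition: "We then conservatively inflate the sample size for an attrition rate of 20% through month24". That leaves 230 × 0.8 = 184 at month 24. Aim 3 uses month-3 mediators and month-6 weight, so its number should lie between 184 and 230. Both ends were examined. Survey non-response at month 3 is not given and is assumed to fall within this range.

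**3. Shape.** For a product of two independent normal estimates whose true values are z1 and z2 standard errors from zero, the variance is z1² + z2² + 1 and the third central moment is 6·z1·z2. Skewness is therefore 6·z1·z2 / (z1² + z2² + 1)^1.5. It is zero if either path is zero, positive in the direction of the effect if both are present, and small if one is much larger than the other. With both at zero the product is symmetric but sharply peaked. Summing five products dilutes the skewness.

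**4. Simulation.** The regressions of Section 10.2 were simulated with 1:1 arms, 1,000 bootstrap draws per data set and 2,000 to 4,000 data sets per scenario, without baseline covariates or small-group clustering. The same draws gave (a) estimate ± 1.96 bootstrap SE and (b) the 2.5th and 97.5th percentiles. Arm effects (d, in SD), mediator slopes (a, in residual SD of weight) and mediator correlation (r) are assumptions.

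Power (%) for the joint five-mediator effect, SE interval → percentile limits:

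| Scenario | N = 184 | N = 230 |
|---|---|---|
| d 0.28, a 0.05, r 0.5 | 12.4 → 17.8 | 21.4 → 29.8 |
| d 0.28, a 0.10, r 0.5 | 43.4 → 50.0 | 61.1 → 66.8 |
| d 0.40, a 0.08, r 0.5 | 61.8 → 69.3 | 79.5 → 84.6 |
| d 0.50, a 0.05, r 0.5 | 41.1 → 47.3 | 56.6 → 63.6 |
| d 0.28, a 0.10, r 0 | 50.4 → 58.4 | 66.7 → 72.9 |
| slopes of mixed sign, d 0.40 | 43.0 → 49.9 | not run |
| one active slope (0.3), d 0.40 | 34.8 → 41.2 | not run |
| slopes dominate: d 0.28, a 0.30 | 66.2 → 67.3 | not run |
| arm effects dominate: d 0.80, a 0.05 | 61.3 → 65.4 | not run |

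The gain is about 5 to 8 points, and 1 to 4 in the last two rows. The simulation error of one power figure is at most √(0.25/2000) = 1.1 points. Both methods are scored on the same data, so the error of a 7-point gain is nearer √(0.07 × 0.93/2000) = 0.6 points if nearly all disagreements run one way. Mean bootstrap skewness was 0.2 to 0.3 in most non-null cases, 0.05 when the slopes dominate, and about 0 under the nulls.

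**5. In kilograms.** A second simulation used a residual SD of 5 kg, five mediators correlated 0.5, 1,500 data sets and 600 draws. For comparison, "we anticipate a common standard deviation of 19.9 kg" with correlation 0.96 gives a residual SD of 19.9 × √(1 − 0.96²) = 5.6 kg at month 24. A true indirect effect of 5 × 0.4 × (−0.3) = −0.60 kg gave 37% → 48% at N = 184 and 55% → 63% at N = 230. The same −0.60 kg from 5 × 0.3 × (−0.4) gave 38% → 46% and 54% → 60%. At −0.38 kg: 13% → 20% and 25% → 32%. At −0.80 kg: 62% → 71% and 81% → 86%. The gains are 5 to 9 points, with one of 11.

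**6. Validity.** Under five-mediator nulls in the first simulation, the SE interval rejected in 0.1% to 4.5% of data sets and percentile limits in 0.2% to 4.7%. Coverage of non-null effects was 95.5% to 98.7% and 95.4% to 98.1% respectively.

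**The case against.** The strongest reply is that Section 10.2 states how standard errors are obtained and no more. It names no test, and Aim 3 is framed as estimating an extent. Bootstrapping the standard errors does not rule out percentile limits from the same draws. This stands in part: a reader might infer that the plan forces, or has chosen, a normal-theory test, and the text does not say so. The symmetric interval is only what a plan that supplies standard errors alone implies. That still makes the sentence worth completing, because followed as written it leads to the weaker interval.

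Other readings also go too far:

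- *The test runs far below its nominal level.* This holds only when both sets of paths are zero or small. With no arm effect and slopes of 0.3, the SE interval rejected in 4.5%. When all paths are zero, percentile limits are conservative too (0.2% to 0.3%), so the change does not cure that.
- *About 184 completers fix the power.* That count belongs to month 24, not to the month-6 outcome of Aim 3. The gain persists at 230, but the power levels differ.
- *The direct effect suffers as well.* It is one regression coefficient, and no defect was shown.

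Finally, every power figure rests on path sizes and correlations that the documents do not give, and the first simulation left out baseline covariates and clustering. This limits the size of the claim. The direction was the same in every non-null scenario tried.

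**Conclusion.** The point holds as a free improvement to an exploratory analysis. Under the assumed paths and 184 to 230 analysable patients, percentile limits gain typically 5 to 9 points of power for the joint indirect effect, and 1 to 4 when one set of paths dominates. There was no inflation of type I error above 5% with five mediators and no material loss of coverage. The result should not be carried over to single products: with one mediator, percentile limits rejected in 5.6% to 6.0% under the null, so part of the larger gain there (7 to 19 points) is spent alpha. A reader might infer that the present wording makes a negative mediation finding likely. The documents do not support that, since they give no path sizes and name no rejection rule. The primary conclusion on 24-month weight is untouched.

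**What to change.** Add to Section 10.2, Aim 3, after the sentence on standard errors: *The 95% confidence interval for the natural indirect effect is the 2.5th to 97.5th percentile of at least 2,000 bootstrap draws; the resampling unit is [patients / small groups].* The direct effect may keep its bootstrap standard error. The choice of unit should be made explicitly: resampling patients ignores the within-group correlation that Section 10.1 allows for, while resampling groups draws from only about 20 units (230/11.5, from the planned 11 to 12 patients per group). No decision rule need be added to an exploratory objective. The cost is one sentence and no computation beyond the bootstrap already planned.

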### Patient weight loss initiation intervention (months 1-6, both arms)

Groups of ~11-12 patients will meet every 2 weeks and will be led by an interventionist. Meetings will begin with weigh-ins by research staff (self-report weight photos may be collected via a DOS REDCap link if group classes are delivered remotely and participants will be mailed a scale in this situation) and will involve dietary education, physical activity demonstration, and goal setting. Partners in the partner-assisted arm will attend a subset of these sessions, whereas partners in the patient-only arm will not be permitted to attend group sessions. The group sessions may be delivered via a video call if necessary due to public health measures that would prevent classes from happening in-person. Patients will download the MyFitnessPal application to their mobile phones, to promote

self-monitoring of diet. Although patients will be recruited in Madison, WI, where the PI is located, data from the Fitbit™ will be transmitted to Prompt, a mobile health platform developed by the Duke Digital Health Institute. Using Prompt will save time and money that would be needed to develop a similar resource at UW. Study staff will assist patients during the first group meeting with installing the apps and will be available for ongoing support throughout the trial.

We have reported the theoretical orientation of the initiation and maintenance interventions.(75) The constructs and way they are operationalized are summarized in Table 4. Although the didactic content varies across contacts, the same initiation behavioral strategies are taught and practiced in each group session in months 1-6, and the same maintenance strategies are taught and practiced in each contact in months 7-18. Our model addresses social support during initiation and maintenance.(75) During initiation, patients in a group-based weight loss intervention may receive support from two sources: (1) the intervention setting (interventionist, group members) and (2) their existing social network (friends, family, coworkers). Regarding (1), patients in both arms may derive support from the intervention setting. Regarding (2), in the patient-only arm, patients will not receive instruction on how to solicit social support and partners will not receive intervention. In the partner-assisted arm, couples will receive training in how to engage in communal coping. All the in-person group sessions will be audio recorded.

Table 4

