**Aim 1: Test the hypothesis that average patient weight is at least 2.5 kg lower in the partner-assisted arm than the patient-only arm at 24 months.** The unit of time will be months relative to randomization. The outcome is weight measured at each in-person study visit. Therefore, *month0* represents the weight at the point of randomization (i.e., the first group visit), and *month24* represents the primary study endpoint. The between-arm comparison in net weight loss from *month0* to *month24* will be examined with a multilevel longitudinal model(80) of the general form:  $Y_{ijt} = X_{ijt}\beta + c_j + Z_{ijt}b_{ij} + \varepsilon_{ijt}$ , where  $Y_{ijt}$  is weight in kg for patient  $i$  in small group  $j$  at  $t=month0, 6, 12, 18, 24$ . The predictors in the model will ( $X_{ijt}$ ) include a time main effect, the intervention main effect, and the intervention arm by time interaction, and  $Z_{ijt}$  will include an intercept and a time effect. We will use a flexible polynomial model for the main effect of time and keep the treatment by time interaction linear in time. We will first explore cubic time effects. If it is inadequate for the complexity in the temporal trend, higher order polynomials will be explored. We will formally check for the adequacy of a particular form for time effects using Wald or likelihood ratio tests for higher-order terms. The effect  $c_j$  is an additional random intercept for small group  $j$ , capturing common effects at the small group level. The predictor vector  $X_{ijt}$  will also include indicator variables for each of the eight strata defined by the cross-classification of the stratification variables of patient sex, patient BMI, and partner BMI. As a first step, the correlation of patients' repeated measures over time will be modeled and accounted for via the patient-level random intercept and time slope,  $b_{ij}$ . However, as is advised by good modeling practice,(80) various covariance structures for time will be explored, including unstructured and differential correlation structures by arm, via graphics such as the variogram and estimation with ReML,(81) all while being blinded to treatment effects. The AIC and BIC fit indices will be used to choose the best correlation structure. We will estimate the parameters in the model using the SAS procedure MIXED (Cary, NC). To test the null hypothesis that the average weight is equal in the two intervention arms, we will test if the coefficient for the time by treatment interaction is zero. Specifically, if  $X_{ijt}\beta$  takes the following form  $\beta_0 + \beta_1 trt + \beta_2 time + \beta_3 trt * t + \beta_4 covariates$ ,

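### Aim 3 specifies no handling of small-group clustering: the mediation regressions have no group term and the bootstrap unit is not stated

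*Combined protocol and SAP*

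**What the plan says.** Under Aim 3 in Section 10.2, the effect of arm on month-6 weight "is jointly mediated by a vector of five mediating constructs" measured at month 3. The direct and indirect effects are obtained "by estimating a set of regression equations": one for weight given arm, mediators and baseline covariates, and one for each mediator given arm and baseline covariates. All carry the patient index only. The covariates are baseline values "of the blocking variables, weight, and the mediating constructs"; small group is not among them. On precision there is one sentence: "We will bootstrap the standard errors for the direct and indirect effects".

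Elsewhere the plan treats clustering as real.

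- **Sample size (Section 10.1):** the target is inflated to "incorporate the intra-class correlation (ICC) of small group members into consideration", with ICC 0.01 and 15 patients per group.
- **Aim 1 (Section 10.2):** patients are indexed within small groups. The model has a term that "is an additional random intercept for small group", described as "capturing common effects at the small group level".
- **Aim 2 (Section 10.2):** it takes over the Aim 1 models.
- **Delivery (Section 9.2.2):** "Groups of ~11-12 patients will meet every 2 weeks and will be led by an interventionist". Section 9.2.1 ties the group date and time to the randomized assignment, and Section 9.2.2 bars partners in the patient-only arm from the sessions. Arm is therefore constant within a group, although no single sentence says so.

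**The concern.** When arm does not vary within a group, every effect of arm is a contrast between groups. That covers the arm coefficient in the weight equation (the direct effect) and the arm coefficients in the five mediator equations, which feed the indirect effect. Variation between groups is then part of the error of those estimates. Resampling individual patients does not reproduce it.

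Clustering is plausible at the Aim 3 time points. Month 3 falls within the biweekly group sessions and month 6 at the end of the initiation phase. In the partner-assisted arm, shared sessions deliver the communication training and role plays aimed at the mediators. If between-group variance is left out, chance differences among about 10 groups per arm could be read as a direct effect of the intervention or, less readily, as mediation.

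**Working it through.** **1. The plan's own clustering figures.** Inputs from Section 10.1: difference 2.5 kg, SD 19.9 kg, correlation 0.96, 80% power, 5% type I error (two-sided reproduces the result).

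- Per arm: 2 × [19.9 × (1.960 + 0.842) / 2.5]² = 995. Times 2(1 − 0.96) = 0.08 gives 79.6, so 80 per arm and 160 in total (162 with the extra participant per arm).
- Design effect: 1 + (15 − 1) × 0.01 = 1.14, and 160 × 1.14 = 182.4 (plan: 180).
- Attrition of 20%: 180 / 0.8 = 225, or 182.4 / 0.8 = 228 (plan: 230).

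The chain reproduces to within about 3%. The plan gives no corresponding figure for Aim 3.

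**2. Number and size of groups.** Section 8.5.1 gives 5 cohorts of about 46 couples. With 11.5 patients per group, 46 / 11.5 = 4 groups per cohort, so 20 in all and 10 per arm. The group size analysed is between 11.5 × 0.8 = 9.2 (full 20% attrition) and 11.5.

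**3. Analytic size for an effect of arm.** Design effect DE = 1 + (m − 1) × ICC. A patient-level standard error is too small by 1 − 1/√DE. The true size of a nominal 5% test is 2[1 − Φ(1.96/√DE)]. Only ICC 0.01 comes from the plan; 0.02 and 0.05 are assumed.

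| ICC | m | DE | SE too small by | True type I error |
|---|---|---|---|---|
| 0.01 | 9.2 | 1.082 | 3.9% | 6.0% |
| 0.01 | 11.5 | 1.105 | 4.9% | 6.2% |
| 0.02 | 9.2 | 1.164 | 7.3% | 6.9% |
| 0.02 | 11.5 | 1.210 | 9.1% | 7.5% |
| 0.05 | 9.2 | 1.410 | 15.8% | 9.9% |
| 0.05 | 11.5 | 1.525 | 19.0% | 11.2% |

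**4. Simulation of the two planned effects.** The formula does not apply directly to a sum of products, so the five-mediator model was simulated with 20 groups of 10 and no effect of arm. At 1,000 trials the Monte Carlo error of a 5% rejection rate is √(0.05 × 0.95 / 1000) = 0.7 points. Ranges are across separate runs.

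- *Direct effect, patient bootstrap, normal cut-off:* rejection 4.7-5.8% at ICC 0, 6.2-6.8% at 0.01, and about 10-11.8% at 0.05.
- *Joint indirect effect, patient bootstrap:* standard error adequate at 0.01 and 6-10% too small at 0.05.
- *Direct effect, group bootstrap, ICC 0.01:* 7.2-7.5% with the normal cut-off; 5.1% and 6.2% in two runs with t on 18 df. The patient bootstrap with the t cut-off gave 4.6%.
- *Direct effect, group bootstrap with t, ICC 0.05:* 6.2%, against 10.5% for the patient bootstrap in the same run.

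A simpler simulation (one mediator, assumed paths 0.4 and 0.3, 20 groups of 11, ICC 0.05) gave true standard errors of 0.165 (direct) and 0.059 (indirect), against 0.137 and 0.050 from the patient bootstrap. The shortfalls are 1 − 0.137/0.165 = 17% and 1 − 0.050/0.059 = 15%. The indirect-effect shortfall therefore depends on the assumed paths.

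**The case against.** **The equations do not assume independence.** A reader might infer that the plan declares patients independent or resamples them individually. The documents support neither. The Aim 3 equations are conditional means, which a group random intercept would leave unchanged, and the bootstrap sentence names no unit. This objection stands, and it limits the point to what is not specified. It does not remove the point: the Aim 1 model writes the group term out, Aim 3 does not, and an analyst following Aim 3 literally would resample patients. Section 18 lists a Statistical Analysis Plan as an attachment, but nothing in the text available adds clustering to Aim 3.

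**The effect is small at the only ICC the plan gives.** This also stands. At 0.01 the indirect effect, which is what Aim 3 is about, is hardly touched. The plan sets no alpha or decision rule for Aim 3, so the type I error figures are best read as a measure of interval under-coverage.

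**Couple skills are taught in one arm only.** If mediator clustering arose solely from that teaching, the design effect would average with 1. At ICC 0.05 it would be (1 + 1.41)/2 = 1.205 to (1 + 1.525)/2 = 1.263, a shortfall of 9-11% in place of 16-19%. This is a fair limit for the mediator paths. It is weaker for weight, because both arms meet in interventionist-led groups and the plan's own group term covers both.

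**Group resampling alone is no remedy.** This stands at ICC 0.01, where it showed no gain; the lower rates there come from the t cut-off. The gain appears at about 0.05.

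**Conclusion.** The point holds as a gap in specification with a modest numerical effect. Aim 3 has no small-group term and no stated resampling unit, although arm is constant within groups and the other two aims model the groups.

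Under a default patient-level bootstrap at the plan's ICC of 0.01, the direct-effect standard error is about 4-5% too small (type I error about 6-6.5%) and the joint indirect-effect standard error is adequate. At an assumed ICC of 0.05, the direct-effect standard error is nearly a fifth too small (type I error about 10-12%). The joint indirect-effect standard error is then about 5-10% too small in the five-mediator model without an arm effect.

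These sizes rest on about 20 groups of 9 to 12 patients, similar clustering in both arms, and an ICC that the documents do not give for the mediators.

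A reader might go further and infer that the mediation findings would be unreliable or that the trial's main result is at risk. Neither follows. The larger errors need an ICC about five times the plan's value, Section 6 labels the mediator objective exploratory, and the Aim 1 and Aim 2 models already carry the group term. This is a minor-to-moderate correction.

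**What to change.** Amend Aim 3 in Section 10.2 in three respects.

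1. Add the small-group random intercept from Aim 1 to the weight equation and to each mediator equation.
2. Replace the bootstrap sentence with one that names the unit, for example: standard errors for the direct and indirect effects will be obtained by resampling whole small groups within arm and refitting the models.
3. State a small-sample reference, such as t with (number of groups − 2) degrees of freedom. With 20 groups that is 18 df and a critical value of 2.10. It is needed because a plain group bootstrap with about 10 groups per arm is itself too narrow: in the one-mediator simulation its normal-based intervals covered about 91-93%.

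Reporting the estimated ICC for month-6 weight and for each mediator would show which part of the range applies.

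The change needs no new data or participants. Intervals become slightly wider and less stable with so few groups. The t reference is also an approximation for a sum of products: with group resampling it can be conservative for the indirect effect, with rejection of about 3-4% in simulations at ICC 0.05 to 0.10.
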